# 2. Data storage/maintenance of subject confidentiality

# Patient Privacy and Data protection:

The data collected will be kept on an encrypted database accessible only to the PI ([name]) caring for the patients enrolled in the study and to the research personnel that is indicated in the IRB. Informed consent forms, patient reported surveys (questionnaires) will be kept in locked storage cabinets in locked room in Orthopaedic Suregry Department ([name]). When the research data is transferred to digital media, we will de-identify the patients records and will use codes only. The data will not be used for any future study.

# 3. Monitoring:

This is a single site study with low number of enrollment, PI ([name]) and the research team will be responsible for data monitoring and progress of the study in accordance with GCP guidelines

# 4. Data analysis

We hypothesize that IFC therapy will improve patient's pain management and range of motion as well as decrease soft tissue edema after TKA when compared to control group. Study variables: total opioid consumption per 24h and 48h, VAS pain scale, KOOS pain score, range of motion, thigh circumference, 6-click AMP scores.

The significance level of the test was targeted at 0.05.

All outcomes and PT exam measures will be summarized as mean, standard deviation, and range. Differences between means will be analyzed with a Student's t-test or Mann-Whitney U test.

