Enrolled patients will be randomly assigned to either **i. IFC treatment or ii. Placebo group** after their surgery. Patients in both groups will continue their regular standard post-operative care in addition to the IFC (or placebo) treatment. In addition to their post-operative standard of care, both groups will receive IFC treatment (or Placebo treatment) two times a day, for two days during their post-op hospital stay.

i. For the IFC treatment group: In addition to their post-operative standard of care, the IFC group will receive IFC treatment two times a day, for two days during their post-op hospital stay. The specific intensity of the IFC signal is patient specific. We will use previously established intensity values for each patient.

Once the intensity is set the program will lock automatically after 1 minute of inactivity or can be manually locked using the "star" button on the device. There is some degree of subjectivity in this portion but that is what provides the user with a patient specific signal. The signal intensity can go up to "100" on the device. The device works for 30 minutes at a time. On the device there is a timer which shows the time and it will automatically turn itself off after 30 minutes. During the time when the device is working, the patient can do any regular activity such as ambulating, physical therapy or sleep without concern.

The electrode has an adhesive pad that can remain on the patient post-operatively if desired or can be removed and replaced for each treatment session. The individual electrodes are re-usable and will be assigned to each patient.

For Placebo group: The standard of care and their physical therapy will not be altered for the placebo group. One set of the devices are programmed to be the placebo devices. The placebo devices can give a sensory stimulus so that the patient will feel the device is being on, but they will not have the therapeutic stimulus. We will monitor and record the same post-surgery outcomes as for the treatment group.

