The outcomes will be monitored in the immediate post-operative period by the Orthopaedic Surgery clinical team at Wakefield Hospital as well as at during the first post-op visit by [name] office by physician assistant ([name],PA) and nurse practitioner ([name]). The average hospital stay for TKA patients in the hospital (Wakefield) varies between 48-72 hours post-operatively. Typically, patients have a follow-up visit at 2 weeks and 6 weeks after surgery in the Hutchinson Campus, Tower 1 Orthopaedic Surgery Department clinic.

1. Primary outcome will be the post-operative pain medication usage during the first 24 and 48 hours. Daily opioid use will also be accounted based on electronic medical record reported by the patient's nurse after providing the patient with the specific medication. In addition, patients will be asked to rate their pain based on a set VAS pain scale twice a day before the IFC treatment.

2. Secondary outcomes Fitness for discharge on postoperative day 1and day 2 this will be measured utilizing the AM-PAC "6-Clicks" Basic Mobility Inpatient Short Form. The "6-Clicks" tool measures functional ability by having an assessor rate a patient's ability to perform physical tasks such as turning over in bed, moving from a bed to chair, and climbing steps. Scores are tallied to a total of 24 possible points, giving a quantitative measure of a patient's ability to perform these tasks. We will also use the `time` to reach the discharge as the outcome, pain scores recorded by nursing and physical therapy, complications, and any 30-day post discharge emergency department ED visits. Range of motion will be recorded during the daily physical therapy sessions by PT professionals with a goniometer. Range of motion then be assessed again in clinic at the first post-operative visit. Edema- thigh circumference will be calculated at the superior pole of the patella both prior to the surgery and daily post-operatively.All these outcome scores are done routinely as standard of care and they are recorded in patients charts in EPIC.

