# b. Power/sample size

We will need a sample of 50 subjects in each group to have 80% power to detect a 30% reduction in mean 48 hour opioid use at a two-sided 0.05 significance level, assuming a mean 48 hour opioid use of 84.2mg and a standard deviation of 44.7 in the standard of care group. For this study, we anticipate to start with 25 patients per group.

Drop out/loss to follow up rate: If any patient who is assigned to treatment group decides to leave the study for any reason or any point of the study, they will be dropped out of study. Similarly, if the patient does not show up to post-operative follow up, they will be dropped from the study. The post-op follow up rates are almost at 100%, so we do not anticipate to have more than 10% drop-off. After any potential drop-offs, we aim to have 20 subjects per group at the end of this study.

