## **Randomization**

Prior to surgery in the clinic visit, patients will be given the The Pain Catastrophizing Scale, PCS short form. Based on the results of surveys, we will only include patients with Mild or Moderate anxiety towards pain. Eligible patients will be asked if they would enroll in the study. The survey will allow the opportunity to find a homogenized patients group for treatment and control groups.

Enrolled patients will be randomly selected into `IFC treatment` or `Control` groups after their surgery. This will enable us to eliminate any possible surgical bias.

We will use block randomization for this study: the surgeon and study group will not interfere in the randomization process to eliminate possible bias. Participants will be randomized in a 1:1 ratio (treatment:placebo). A block randomization scheme with a block size of 6 will be generated and maintained by the study statistician. The statistician will provide the sites with a set of randomization envelopes to be used in the study clinics. The randomization envelopes will be stored by the study coordinators in a locked cabinet. Study staff, not including the investigator who will perform clinical evaluations after surgery, will assign these envelopes in sequential order, by envelope number, to eligible participants. Each randomization envelope will include study treatment arm randomization assignment. Assignment of the randomization envelope is considered the effective act of participant enrollment/randomization.

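### The analysis section makes no use of the pre-surgery thigh circumference and does not say whether a VAS rating taken before any session counts as outcome; settling both is an optional, low-cost gain in precision

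*Combined protocol and SAP*

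**What the plan says.** Section 4, Data analysis (under Data and Safety Monitoring), lists the variables: "Study variables: total opioid consumption per 24h and 48h, VAS pain scale, KOOS pain score, range of motion, thigh circumference, 6-click AMP scores". It then gives one method for all of them: "Differences between means will be analyzed with a Student's t-test or Mann-Whitney U test". Neither that section nor any other names a covariate, a change score, a post-operative day for circumference, or a rule for combining repeated VAS ratings.

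The measurements are described under Study Design. In the secondary outcomes, "thigh circumference will be calculated at the superior pole of the patella both prior to the surgery and daily post-operatively". VAS appears in the primary-outcome paragraph as an addition to opioid use: patients "rate their pain based on a set VAS pain scale twice a day before the IFC treatment". Treatment is given "two times a day, for two days during their post-op hospital stay".

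The Randomization section puts patients into "groups after their surgery. This will enable us to eliminate any possible surgical bias". The pre-surgery circumference is therefore a pre-randomisation value. The documents do not say whether the first VAS rating comes before or after the randomisation envelope is opened.

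The Power/sample size section sizes the trial to "detect a 30% reduction in mean 48 hour opioid use at a two-sided 0.05 significance level" and to nothing else. On completers it says "we aim to have 20 subjects per group at the end of this study".

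**The concern.** Reduced soft-tissue edema is part of the stated hypothesis, and thigh circumference is its measure. Thighs differ in size between patients whatever the treatment. A comparison of raw post-operative values carries all of that variation, and the pre-surgery value could remove some of it. The plan also leaves open whether raw values or changes are tested, and on which day. With about 20 patients per group these choices can give different answers, and nothing prevents them from being made after the data are seen.

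For VAS the issue is narrower. A rating taken before the first session cannot reflect treatment. If it is averaged into the outcome, it dilutes any effect. If change from it is tested, its noise is added to the result. The plan neither defines it as a baseline nor excludes it.

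What is at stake is precision on two non-primary measures, and some freedom of choice in the analysis. The validity of the comparison is not at stake.

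**Working it through.** **The plan's own figure.** From the Power/sample size section: control mean 84.2 mg, SD 44.7, reduction 30%, so the difference is 0.30 × 84.2 = 25.26 mg. Then n = 2 × (1.960 + 0.842)² × 44.7² / 25.26² = 49.2, which rounds up to 50 per group, as stated. It concerns opioid use only. No circumference or VAS figure is given, so the effect size and all correlations below are assumptions.

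**Circumference.** Inputs: 20 per group (from the plan), two-sided 0.05, effect 0.5 SD (assumed), correlation r between pre-surgery and post-operative values (assumed), equal SDs at both times (assumed). Power comes from the noncentral t with noncentrality 0.5 / √(2V/20), where

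- raw values: V = 1, 38 df;
- change scores: V = 2(1 − r), 38 df;
- ANCOVA: V = (1 − r²) × 37/36, 37 df. The factor (N − 3)/(N − 4) with N = 40 is the cost of estimating the slope.

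Example at r = 0.7: ANCOVA V = 0.51 × 37/36 = 0.524, noncentrality 2.18, power 56.6%.

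| r | Raw | Change | ANCOVA | ANCOVA − raw | ANCOVA − change |
|---|---|---|---|---|---|
| 0.3 | 33.8% | 25.6% | 35.7% | 1.9 | 10.1 |
| 0.5 | 33.8% | 33.8% | 41.9% | 8.1 | 8.1 |
| 0.7 | 33.8% | 51.2% | 56.6% | 22.8 | 5.5 |
| 0.8 | 33.8% | 68.3% | 71.6% | 37.8 | 3.3 |
| 0.9 | 33.8% | 93.1% | 93.6% | 59.8 | 0.5 |

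(Differences are in points, taken before rounding.)

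Break-even with raw values: (1 − r²) × 37/36 = 1 gives r = √(1/37) = 0.16. At r = 0, ANCOVA has 33.0% against 33.8%, a loss of 0.8 point. A simulation of the variance ratio of ANCOVA to the unadjusted difference (15,000 trials per setting) gave 1.026, 0.938, 0.771 and 0.194 at r = 0, 0.3, 0.5 and 0.9. The formula gives 1.028, 0.935, 0.771 and 0.195.

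**VAS.** Assume one rating before each of 2 × 2 = 4 sessions and a constant 0.5 SD effect on ratings 2-4. Let ρ be the correlation among ratings 2-4, and q that between rating 1 and each of them. With V3 = (1 + 2ρ)/3:

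- mean of all four: effect 0.75 × 0.5 = 0.375 SD, V = (1 + 9·V3 + 6q)/16, 38 df;
- mean of 2-4: V = V3, 38 df;
- mean of 2-4 adjusted for rating 1: V = (V3 − q²) × 37/36, 37 df;
- change from rating 1: V = V3 + 1 − 2q, 38 df.

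Rating 1 predicts later pain weakly (ρ = 0.5, V3 = 0.667):

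| q | Mean of four | Mean of 2-4 | Adjusted | Change | Adjusted − mean of 2-4 |
|---|---|---|---|---|---|
| 0 | 41.6% | 47.1% | 46.0% | 22.3% | −1.1 |
| 0.1 | 38.9% | 47.1% | 46.6% | 24.7% | −0.5 |
| 0.2 | 36.5% | 47.1% | 48.4% | 27.8% | +1.3 |

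A simulation (60,000 runs) gave 46.3, 46.6 and 48.3% adjusted, against 47.4, 47.0 and 47.0% for the mean of 2-4.

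If instead q = ρ = 0.3, 0.5, 0.7, power is 38.9, 31.0 and 25.9% for the mean of four; 56.0, 47.1 and 40.6% for the mean of 2-4; and 62.6, 65.3 and 77.9% adjusted.

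**The case against.** The strongest reply is that nothing is broken. Under randomisation the t-test and the Mann-Whitney test are valid without covariates, neither measure was used to size the trial, and an efficiency gain on an unpowered outcome is a preference. That stands, and it sets the severity.

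Second, the large circumference gains arise only against raw values. The hypothesis is about reduced edema and a pre-surgery value is collected, so change from that value is at least as natural a reading. Against change scores, ANCOVA gains only 5.5, 3.3 and 0.5 points at r = 0.7, 0.8 and 0.9. This also stands. What remains is that the plan does not choose, change scores lose about 8 to 10 points at r = 0.3 to 0.5, and ANCOVA does not require guessing the correlation.

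Third, the VAS baseline is weak. Rating 1 is post-operative, may be taken under residual block (the exclusion criteria require that patients can have a nerve block or spinal anesthesia, and the Risks section anticipates diminished sensation after surgery) and may follow opioid dosing. Its order relative to randomisation is not stated. This stands too, and is why adjustment for it is left optional.

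A reader might infer that both covariates are free gains. They are not: when the correlation is near 0, ANCOVA costs about 1 point at 20 per group. A reader might also infer that the plan will average all four VAS ratings, or test change from the first. No section says so; the plan is silent.

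**Conclusion.** The point holds as an optional improvement. For circumference, ANCOVA on the pre-surgery value gives the highest power of the three analyses at every assumed correlation from 0.3 to 0.9, and loses less than 1 point to raw values below about 0.16. For VAS, the supported conclusion is that a rating taken before any session should not count as outcome. If rating 1 correlates 0 to 0.2 with later ratings, leaving it out gives 47.1%, against 36.5 to 41.6% with all four averaged. Adjusting for it then changes power by only −1.1 to +1.3 points, with a larger gain only at higher correlations.

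All of this rests on an assumed 0.5 SD effect, assumed correlations, 20 per group and, for VAS, one rating before each of four sessions.

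Two stronger readings are not supported. The planned tests are not biased or invalid. Nor do the documents give any ground to expect these covariates to help the primary opioid comparison. The gap between the 50 per group required and the 20 aimed for is a separate and larger matter for that outcome, and this change does not address it.

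**What to change.** In section 4, Data analysis:

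1. State that post-operative thigh circumference, on one named post-operative day, is compared between groups by ANCOVA with the pre-surgery value as covariate. Add how a missing pre-surgery value is handled, so that patients are not lost to a complete-case model.
2. Define the VAS rating before the first session as baseline, taken before the envelope is opened or at least before that session. Define the VAS outcome as the mean of ratings 2-4. Say whether the baseline is a covariate; either choice is acceptable if made in advance. Give a rule for skewed ratings, since the present text leaves the t-test or Mann-Whitney choice open.

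The cost is a few sentences and minor programming, with no new visits or measurements. The one procedural addition is fixing when the first VAS rating is taken. The wording should be settled before any unblinded analysis.

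### Outcomes read several times per patient are given only a two-sample test; the plan should name one comparison for each, using baseline where it is measured

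*Combined protocol and SAP*

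**What the plan says.** The Study Design section (primary and secondary outcomes) sets the readings:

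- **VAS:** "patients will be asked to rate their pain based on a set VAS pain scale twice a day before the IFC treatment". Treatment is given twice a day for two days, which implies four ratings, the first before any treatment.
- **Range of motion:** "Range of motion will be recorded during the daily physical therapy sessions by PT professionals with a goniometer", and once more at the first post-operative clinic visit.
- **Thigh circumference:** before surgery and on each post-operative day.
- **6-Clicks:** post-operative days 1 and 2.

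The same section gives a usual stay of 48 to 72 hours, so the number of daily readings can differ between patients.

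Section 4, Data analysis, is the whole analysis plan. It lists these four outcomes among the study variables and states "All outcomes and PT exam measures will be summarized as mean, standard deviation, and range", then "Differences between means will be analyzed with a Student's t-test or Mann-Whitney U test". On error control it says "The significance level of the test was targeted at 0.05". Neither it nor any other section says which reading is compared, how readings are combined, whether the baseline values are used, or how several tests of one outcome are handled.

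**The concern.** Both named tests take one independent value per patient, and the plan does not say what that value is for any of the four outcomes. The choice is left until the data are in hand. Two natural readings of the sentence each carry a cost: a test at every time point raises the chance of a false positive for that outcome, and a test at one time point gives up precision.

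Pain, range of motion and edema make up the hypothesis stated in Data analysis, and VAS is described under the primary-outcome heading. The trial expects to start with 25 per group and finish with 20, so it has little precision to spare. The plan also collects a pre-treatment VAS rating and a pre-operative circumference, both usable as covariates, and assigns them no role.

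**Working it through.** **1. The plan's own figure.** The sample-size section asks for "80% power to detect a 30% reduction in mean 48 hour opioid use at a two-sided 0.05 significance level". Its control-arm inputs are 84.2 mg (mean) and 44.7 (SD). The difference is 0.30 × 84.2 = 25.26 mg. Then n = 2 × (1.96 + 0.8416)² × 44.7² / 25.26² = 49.2, rounded up to 50 per group (50.1 with the t distribution). This agrees with "We will need a sample of 50 subjects in each group". It rests on the 48-hour opioid total, one value per patient, so nothing below alters it.

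**2. Inputs for the repeated outcomes.**
- From the documents: 25 per group at the start and 20 at the end; four VAS ratings, three of them after the first session; two-sided 0.05.
- Assumed, because the documents give no figure: equal correlation ρ between a patient's readings, 0.4 to 0.6, with 0.9 as a high case; a true effect of 0.5 SD for the power figures.

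**3. A separate test at each reading.** With independent readings, the chance of at least one false positive in three tests is 1 − 0.95³ = 14.3%. Correlation lowers this. Simulation with no true effect (20,000 trials, normal readings, 20 and 25 per group) gives about 12 to 13% for ρ = 0.4 to 0.6, and about 8 to 9% at ρ = 0.9. One t-test on the per-patient mean gives 5.0 to 5.2% at ρ = 0.4 and 0.6. Range of motion also has about three readings in a 48-hour stay plus clinic, so the same figures apply under the same assumptions. For two readings (6-Clicks, or circumference on two days) the bound under independence is 1 − 0.95² = 9.8%.

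**4. One reading against the mean of three.** Relative to a single reading, the variance of a three-reading mean is (1 + 2ρ)/3, that is 0.60, 0.73 and 0.93 at ρ = 0.4, 0.6 and 0.9. The standardised effect becomes 0.5/√variance: 0.65, 0.58 and 0.52. Power from the noncentral t:

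| Per group | One reading | Mean of 3, ρ = 0.4 | ρ = 0.6 | ρ = 0.9 |
|---|---|---|---|---|
| 25 | 41% | 61% | 53% | 43% |
| 20 | 34% | 51% | 44% | 36% |

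**5. Adding the first rating as a covariate.** If the first rating correlates with the later ones at the same ρ, the variance of the three-reading mean falls to (1 + 2ρ)/3 − ρ²: 0.44, 0.37 and 0.12 at ρ = 0.4, 0.6 and 0.9. Averaging helps most when correlation is low and adjustment helps most when it is high, so using both covers the range.

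**The case against.** The strongest reply is that the named tests are not wrong. A t-test or Mann-Whitney U test on one summary per patient (a mean, a change or a value at a set time) is valid and fits the sentence as written. That stands, and it limits the point to something left unspecified.

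A reader might infer more in two places. The first is that the plan will pool all readings as if they came from different patients. That would inflate error further, but no section proposes it, so it cannot be charged to the plan. The second is that pain scores charted by nurses and therapists suffer the same fault, with unequal counts per patient. They are not in the list of study variables in Data analysis, and no frequency is given, so the documents do not establish this.

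Other replies have partial force. Most of the affected outcomes are secondary, and unadjusted by-day tests can be acceptable if labelled exploratory; the plan does not label them so, and VAS sits under the primary heading. The correlation and the 0.5 SD effect are assumptions, and at ρ = 0.9 the gain from averaging alone is slight (41% to 43% at 25 per group).

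A blanket instruction to average would also be poor. Averaging range of motion over the stay and the clinic visit mixes two stages of recovery. Averaging whatever daily readings exist lets the time window depend on length of stay, while time to discharge is itself an outcome. The remedy has to fix the days.

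**Conclusion.** The point holds as a gap in specification for the four outcomes with scheduled repeat readings. It does not show that the trial will analyse them wrongly, and it does not reach the opioid totals or the sample-size calculation. Its size depends on the route taken. Testing reading by reading carries a false-positive chance of roughly 12 to 13% for the post-treatment VAS ratings in place of 5%. Testing a single rating costs about 12 to 20 percentage points of power at 25 per group (53 − 41 to 61 − 41) and 10 to 17 at 20 per group (44 − 34 to 51 − 34). These ranges assume equal correlation of 0.4 to 0.6 and, for power, an effect of 0.5 SD; both effects shrink as correlation rises. The change is worth making because it is cheap and uses data already planned.

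**What to change.** In Data analysis, state one pre-specified comparison for each repeated outcome:

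- **VAS:** the mean of the three ratings taken after the first session, adjusted for the first (pre-treatment) rating, by ANCOVA or a matching mixed model, with a 95% confidence interval. The two agree only when ratings are complete, so name which is used if some are missing.
- **Thigh circumference:** a mixed model over fixed post-operative days 1 and 2, adjusted for the pre-operative value.
- **6-Clicks:** the mean of days 1 and 2.
- **Range of motion:** the inpatient value over fixed days 1 and 2, analysed separately from the first clinic visit, with one of the two named in advance as the main comparison.

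Report all other by-day values descriptively. The existing two-sample wording can remain for the opioid totals.

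The cost is a few sentences and standard software, with no added patients, visits or measurements. The drawback is that by-day differences can no longer be claimed as significant.
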